9 ASSESSMENT OF INVESTIGATIONAL MEDICINAL PRODUCT

9.1 PRIMARY ENDPOINT

9.1.1 Primary efficacy endpoint

Pulmonary function testing (PFT) will be performed locally at the time points specified in [Section 1.2](#) and measured by a central laboratory. During the treatment period, the assessment will be completed before IMP infusion. Assessment should continue to be collected for at least up to Week 49, end of PAP, if the patient discontinues the treatment earlier.

The PFT administration protocol is standardized across sites in accordance with ATS/ERS guidelines (2). Per ATS/ERS 2005 quality standards, an adequate test requires a minimum of 3 acceptable FVC maneuvers and acceptable repeatability needs to be met for the largest and next-largest FVC and forced expiratory volume in the 1st second of the FVC maneuver (FEV₁) as outlined in the study manual. Patients may repeat the PFT assessment up to 3 times within the Screening Visit time window in case of failed quality as determined by the central laboratory (refer to [Section 7](#) for details on screening and re-screening conditions). For each PFT assessment, up to 8 efforts may be performed. Patients are not allowed to use noninvasive ventilation during this assessment. The primary efficacy endpoint is the change from baseline to Week 49 in FVC (% predicted) in upright position. FVC will be reported in liters and percent of predicted normal values based on age, gender, race, and height. Global Lung Initiative (GLI) 2012 reference equations will be used for this study (3).

Postbaseline PFT should meet the ATS/ERS 2005 quality standards. However, if no acceptable efforts can be recorded during the upright position PFT with up to 8 efforts, an additional PFT may be scheduled as soon as possible no later than 45 days after this failed planned test, if this is feasible for the patient. The highest acceptable effort will be kept in the database.

In addition, if the patient did not perform the PFT at a planned visit, the patient should be reminded to perform the PFT as soon as possible no later than 45 days after the missed test, if it is feasible for patient to perform the test within this period.

Refer to the study specific manual for instructions on test administration.

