10.3.4 Handling of patients after permanent treatment discontinuation

Patients will be followed-up according to the study procedures specified in this protocol (see [Section 10.1.9](#)), or up to recovery or stabilization of any AE to be followed-up as specified in this protocol, whichever comes last.

Since the primary study comparison is based on intent-to-treat principle using all randomized patients with any study treatment, missing data, especially the key study assessments during the PAP (Week 49) may potentially lead to biased results and challenges in assessing the treatment effect of the study drug. Therefore, all efforts should be made to continue to follow the patients for primary and key secondary endpoints, after a permanent discontinuation of treatment, in addition to the 4-weeks post-treatment safety follow-up. At the minimum, patients should be assessed at their regularly scheduled Week 49 visit (or as close as possible to Week 49 even if it may be outside of visit window) if treatment discontinuation occurred prior to that visit.

All cases of permanent treatment discontinuation should be recorded by the Investigator in the appropriate pages of the e-CRF when considered as confirmed by documenting the reason(s) for treatment discontinuation.

Patients who permanently discontinue study treatment and who will be switched to commercial avalglucosidase alfa will be withdrawn from the study.

In the event that a patient dies, permission will be sought (through a separate informed consent form) for a research autopsy or post mortem research biopsy. Samples collected from these procedures will be used for research purposes only and data will not be included in any study analyses.

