11.4.3 Open-label avalglucosidase alfa long-term follow-up phase

Efficacy data during the extension treatment phase will be summarized descriptively for each of the efficacy parameters through the last visit (up to the end of the extended open-label avalglucosidase alfa long-term follow-up phase). For the primary efficacy endpoint, the effect of switching treatment will be assessed for those patients who switched from alglucosidase alfa to avalglucosidase alfa during the extension period. For patients who receive avalglucosidase alfa throughout the blinded treatment phase, as well as the long-term follow-up phase, long-term effect of avalglucosidase alfa will be assessed.

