1.2 OBJECTIVES

1.2.1 Primary objectives

The primary objective of the study is to determine the effect of avalglucosidase alfa treatment on respiratory muscle strength as measured by FVC % predicted in the upright position, as compared to alglucosidase alfa.

Estimand for this study is defined as the difference between avalglucosidase alfa treatment and alglucosidase alfa in mean FVC % predicted change from baseline to Week 49 regardless of whether intercurrent events have occurred. This estimand corresponds to a ‘treatment policy strategy’.

Analysis method for estimand (estimator) is based on mixed model for repeated measures (MMRM) assuming missing at random (MAR). All observed data during the study that include the data collected after study treatment discontinuation will be used in the analyses.

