2.10.5 Windows for time points

The visit windows for efficacy endpoints specified in [Table 16](#) are defined in following table. For analysis purpose, a larger window (as shown in the last column of [Table 14](#)) will be used. This will be applicable for those analyses requiring visit information.

Table 14 - Study visit nominal visit days and windows for efficacy endpoints

Scheduled Visit	Visit window defined in protocol in study days	Visit window for analysis purpose in study days
Screening/Baseline	Day -14 to -1	(-28, the day before 1st infusion)
Week 13	Day 85 ±14	(the day after 1st infusion, Day 85 +41)
Week 25	Day 169 ±14	Day 169 (-42, +41)
Week 37	Day 253 ±14	Day 253 (-42, +41)
Week 49	Day 337 ±14	(Day 337 -42, the day prior to the 1st ETP treatment or Day 337 + 41 if 1st ETP treatment is missing)
Week 61	Day 421 ±14	(the day after the 1st ETP treatment, Day 421 +41)
Week 73	Day 505 ±14	Day 505 (- 42, +83)
Week 97	Day 673 ±14	Day 673 (-84, +83)
Week 121	Day 841 ±14	Day 841 (-84, +83)

Scheduled Visit	Visit window defined in protocol in study days	Visit window for analysis purpose in study days
Week 145	Day 1009 ±14	Day 1009 (-84, +83)
Week 169	Day 1177 ±14	Day 1177 (-84, +83)
Week 193	Day 1345 ±14	Day 1345 (-84, +83)
Week 217	Day 1513 ±14	Day 1513 (-84, +83)
Week 241	Day 1681 ±14	Day 1681 (-84, +83)
Week 265	Day 1849 ±14	Day 1849 (-84, +83)

The analysis visit will be defined by comparing the actual visit date with the nominal (or target) date and the corresponding analysis window from [Table 14](#) . If more than one non-missing values are assigned to the same visit, then the one closest to the target date will be used in the by-visit analysis. Multiple values on the same date will be averaged first. If two assessments are on different date but equal distance from the target date, the later date will be used.

For the safety analyses (laboratory, ECG and vital signs), the nominal visit will be used for the by-visit type of analyses.

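### SAP Table 14 leaves some late Week 49 efficacy tests (patients with no extension infusion) and all Week 289 efficacy tests without an analysis visit, although the protocol collects both

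*SAP*

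**What the plan says.** **How visits are assigned.** SAP 2.10.5 states: "The analysis visit will be defined by comparing the actual visit date with the nominal (or target) date", using the analysis windows in Table 14. If several values fall in one window, the one closest to the target day is used. Safety data follow a different rule: "For the safety analyses (laboratory, ECG and vital signs), the nominal visit will be used for the by-visit type of analyses".

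**Week 49.** The Table 14 window starts 42 days before Day 337 and runs to "the day prior to the 1st ETP treatment or Day 337 + 41 if 1st ETP treatment is missing". The Week 61 window is "the day after the 1st ETP treatment, Day 421 +41". Week 73 is Day 505 (-42, +83), with no condition on an ETP infusion.

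**What the protocol collects around Week 49.**
- Section 9.1.1 on a missed PFT: "the patient should be reminded to perform the PFT as soon as possible no later than 45 days after the missed test". The same limit applies to a failed test, and section 10.1.8 repeats both.
- Section 10.1.8 has efficacy tests from a missed visit done at the first opportunity, outside the window if necessary, and kept with the visit that was missed.
- Section 10.3.4 wants patients who stopped treatment early assessed at Week 49 "or as close as possible to Week 49 even if it may be outside of visit window".

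**What the SAP says will be analysed.** Section 1.2.1, under a treatment-policy estimand: "All observed data during the study that include the data collected after study treatment discontinuation will be used in the analyses".

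**End of follow-up.** The last row of Table 14 is Week 265, Day 1849 (-84, +83). Protocol 10.1.5.4 and 10.1.5.5 schedule PFT, 6MWT and the adult questionnaires at Week 289. Protocol 11.4.3 commits to descriptive efficacy summaries "up to the end of the extended open-label avalglucosidase alfa long-term follow-up phase", and SAP 2.5.5 to summaries at each study visit.

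**The concern.** The primary model in SAP 2.5.1 has four visit levels: Weeks 13, 25, 37 and 49. A value that Table 14 assigns to none of them is not used, however valid the test. The Day 378 limit applies only to patients with no ETP infusion. Because the extension is open to all patients, these are mainly patients who stopped treatment in the blinded period. Their off-treatment values are the ones a treatment-policy estimand has to include. The FVC and 6MWT responder analyses (SAP 2.5.3.4.1 and 2.5.1.1.2) also count a patient without a Week 49 value as a non-responder, so a valid late test would be scored as a failure.

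For patients who continue, closing Week 49 before the first ETP infusion makes sense, because the comparator arm then changes drug. That reason does not exist for a patient who never receives an ETP infusion.

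For Week 289, what is at stake is the last planned point of the by-visit long-term efficacy description.

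**Working it through.** **1. Target days.** Target day = 7 x (week - 1) + 1. Week 49 gives 7 x 48 + 1 = 337 and Week 265 gives 7 x 264 + 1 = 1849, both as in Table 14. All 14 post-baseline target days reproduce.

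**2. Windows around Week 49 with no ETP infusion.**

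| Row | Window |
|---|---|
| Week 49 | Day 337 - 42 = 295 to Day 337 + 41 = 378 |
| Week 61 | no start day, because there is no first ETP infusion |
| Week 73 | Day 505 - 42 = 463 to Day 505 + 83 = 588 |

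The unassigned stretch is Days 379 to 462, which is 462 - 379 + 1 = 84 days. A test from Day 463 would be labelled Week 73, which is also outside the primary model.

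**3. What the protocol permits.**
- 45 days from the target day: 337 + 45 = Day 382, which is 382 - 378 = 4 days past the window.
- 45 days from the end of the +14-day visit window: 337 + 14 + 45 = Day 396, which is 396 - 378 = 18 days past it.
- Sections 10.1.8 (missed efficacy visits in general) and 10.3.4 set no last day.

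**4. End of follow-up.** Week 265 closes at 1849 + 83 = Day 1932. Week 289 is 7 x 288 + 1 = Day 2017, with a protocol window of Days 2003 to 2031. The earliest in-window Week 289 test falls 2003 - 1932 = 71 days after the last day Table 14 covers. The SAP's own study plan gives 145 + 144 = Week 289, so the row is not missing because of a version difference: the SAP follows amendment 3, which introduced that extension. Nor is the 45-day rule listed among the changes in amendments 4 to 6.

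**5. Size, by assumption.** The documents give no count of late tests. As a yardstick, take a two-sample t-test with SD 5.1, distance from the margin 2.0 + 1.1 = 3.1, and 96 x 0.9 / 2 = 43.2, taken as 43, per arm. Non-inferiority power is 79.6%, matching SAP Table 4. Each further loss of one evaluable patient per arm gives:

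| Lost per arm | Power |
|---|---|
| 0 | 79.6% |
| 1 | 78.6% |
| 2 | 77.6% |
| 3 | 76.6% |

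**The case against.** **On Week 49.** Table 14 is already generous. It keeps any test up to 41 days after target, against a protocol window of 14 days. Measured from the target day, the 45-day rule overshoots it by only 4 days; the 18-day figure needs a test missed or failed on the last permitted day and then repeated at the limit. Some bound is needed, and the +41 makes consecutive 12-week bins. Missing Week 49 values are also stress-tested by the tipping-point, ANCOVA and rank analyses in SAP 2.5.3. All of this stands and limits the size of the problem. It does not remove the conflict: the protocol asks for these tests, the estimand says they will be used, and the date rule drops them.

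A reader might infer that off-treatment data in general are lost and replaced by extrapolation from on-treatment data. The documents do not support that. Protocol 10.1.9 keeps patients who stop early on the Week 13, 25, 37 and 49 assessments, and SAP 2.5.1 uses those values. Nor can the number affected be taken from an expected discontinuation rate. The 3 of 60 LOTS patients without evaluable Month 12 FVC (SAP 1.3.3) are not shown to have had a late test that a window could discard.

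**On Week 289.** A reader might infer that all Week 289 data are lost, for everyone who completes. They are not. Safety data use the nominal visit. Efficacy values can still enter the last-observation summary in SAP 2.5.5. Participation ends earlier where the drug is approved (in Canada, commercially available) before Week 289. Directly enrolled paediatric patients end at Week 241, which Table 14 covers. Protocol section 5 states no long-term objective; the conflict is with the descriptive commitment in 11.4.3, and no hypothesis test depends on it.

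**Conclusion.** Both conflicts hold and can be read directly from Table 14.

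For patients with no ETP infusion, a Week 49 efficacy test on Days 379 to 462 is left out of the primary MMRM and counted as non-response, although the protocol permits or requests it. The number of such tests is unknown, probably small and possibly zero. Even an assumed loss of three evaluable patients per arm would cost about 3 percentage points of non-inferiority power (79.6% to 76.6%). Nothing here shows that the primary conclusion would change. The case rests on consistency: a treatment-policy estimand that promises all observed data should not be implemented with a window that drops requested tests in patients who are mainly those who stopped treatment.

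For Week 289, efficacy values from randomized patients who stay to the end of the extended phase enter no by-visit summary. This is an omission in a descriptive table.

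Both are worth correcting because the corrections are small.

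**What to change.** **Week 49, patients with no ETP infusion.** Preferably, assign a late test to the missed Week 49 visit, as protocol 10.1.8 states, and let that link override the date windows. At minimum, extend the upper limit from Day 378 to Day 396. A Day 396 limit covers the 45-day PFT rule but only partly meets 10.1.8 and 10.3.4, which set no last day. In either case, use the value closest to Day 337. Under the extended limit, an existing value in Days 295 to 378 would be displaced only by an exact tie (Day 295 against Day 379, both 42 days away), where the SAP already takes the later date.

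The cost is a few later Week 49 values: up to 396 - 337 = 59 days after target under the minimum option, possibly more under the preferred one, in patients who would otherwise have a missing value. If the treatment codes have already been released, list the tests done after Day 378 and report the wider rule as a sensitivity analysis.

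**Week 289.** Add a row: Day 2017 (-84, +83). That is Days 1933 to 2100, which joins the Week 265 window (ending Day 1932) without gap or overlap. It needs no new data and can be made at any time before the final database lock.

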2.10.6 Unscheduled visits

Unscheduled visit measurements of laboratory data, vital signs, and ECG will not be included in the by-visit summaries, but will be used for computation of baseline, worst values, and summary of PCSAs.

2.10.7 Pooling of centers for statistical analyses

Investigation of the effects of geographic regions may be performed on an exploratory basis.

3 INTERIM ANALYSIS

No interim analyses are planned during the double-blinded PAP. After the primary analysis for PAP, interim analyses may be performed during the open-label extension period to provide additional information for regulatory purpose. However, those additional analyses after PAP will be considered for supportive purpose.

4 DATABASE LOCK

The database lock for the primary efficacy analyses is planned to be approximately 30 days after last patient last visit in PAP.

The final database lock for the study is planned to be approximately 30 days after the last patient last visit in ETP.

5 SOFTWARE DOCUMENTATION

All summaries and statistical analyses will be generated using SAS Version 9.4 or higher.

7 LIST OF APPENDICES

[Appendix A](#) Potentially clinically significant abnormalities criteria

[Appendix B](#) Schedule of the efficacy assessment

Appendix A Potentially clinically significant abnormalities criteria

Table 15 - PCSA abnormalities (29)

Measures	Adult Criteria	Pediatric Criteria
Liver function tests		
ALT	>3 x ULN >5 x ULN >10 x ULN >20 x ULN	≥3 x ULN ≥5 x ULN ≥10 x ULN ≥20 x ULN
AST	>3 x ULN >5 x ULN >10 x ULN >20 x ULN	≥3 x ULN ≥5 x ULN ≥10 x ULN ≥20 x ULN
Alkaline Phosphatase	>1.5 x ULN	≥1.5 x ULN
Total Bilirubin	>1.5 x ULN >2 x ULN	≥1.3 x ULN
ALT and Total Bilirubin	ALT >3 x ULN and Total Bilirubin >2 x ULN	ALT ≥3 x ULN and Total Bilirubin ≥2 x ULN
Hematology		
White Blood Cell (WBC)	<3.0 GIGAL (non-Black), <2.0 GIGAL (Black), ≥16.0 GIGAL	Birth/0 to 27 days old (Neonates) <4.0 GIGAL >25.0 GIGAL 28 days/1 month to 23 months old (Infants) <4.0 GIGAL >20.0 GIGAL 24 months/2 years to <6 years old (Children) >3.0 GIGAL >16.0 GIGAL

Measures	Adult Criteria	Pediatric Criteria
Lymphocytes	>4.0 GIGAL	6 to <12 years old (Children) <5.0 GIGAL >17.0 GIGAL 12 to 16/18 years old (Adolescents) <4.5 GIGAL >13.5 GIGAL Birth/0 to 27 days old (Neonates) <1.2 GIGAL >17.0 GIGAL 28 days/1 month to 23 months old (Infants) <2.0 GIGAL >13.5 GIGAL 24 months/2 years to <6 years old (Children) <1.0 GIGAL >9.5 GIGAL 6 to <12 years old (Children) <1.0 GIGAL >8.0 GIGAL 12 to 16/18 years old (Adolescents) <0.6 GIGAL >6.0 GIGAL

Measures	Adult Criteria	Pediatric Criteria
Neutrophils	<1.5 GIGAL (non-Black) <1.0 GIGAL (Black)	Birth/0 to 27 days old (Neonates) <4.0 GIGAL (1 day old) <1.5 GIGAL (2 – 7 days old) <1.25 GIGAL (>7 day – 1 month old) >1 ULN 28 days/1 month to 23 months old (Infants) <1.0 GIGAL (1 – 3 months) <1.2 GIGAL (3 – 24 months) >1 ULN 24 months/2 years to <6 years old (Children) <1.2 GIGAL >1 ULN 6 to <12 years old (Children) <1.2 GIGAL >1 ULN 12 to 16/18 years old (Adolescents) <1.2 GIGAL >1 ULN
Monocytes	>0.7 GIGAL	
Basophils	>0.1 GIGAL	
Eosinophils	>0.5 GIGAL or >ULN if ULN ≥0.5 GIGAL	>0.5 GIGAL Or >ULN if ULN >0.5 GIGAL

Measures	Adult Criteria	Pediatric Criteria
Hemoglobin	Males: ≤ 115 g/L (≤ 7.14 mmol/L), ≥ 185 g/L (≥ 11.48 mmol/L) Females: ≤ 95 g/L (5.9 mmol/L), ≥ 165 g/L (10.24 mmol/L) Decrease from Baseline: ≥ 20 g/L (1.24 mmol/L)	Birth/0 to 27 days old (Neonates) < 86 mmol/L or 12.0 g/dL or any decrease > 0.31 mmol/L or 2 g/dL 28 days/1 month to 23 months old (Infants) < 1.40 mmol/L or 9.0 g/dL or any decrease > 0.31 mmol/L or 2 g/dL 24 months/2 years to $< 16/18$ years old (Children, Adolescents) < 1.55 mmol/L or 10.0 g/dL or any decrease > 0.31 mmol/L or 2 g/dL
Hematocrit	Males : ≤ 0.37 v/v, ≥ 0.55 v/v Females : ≤ 0.32 v/v, ≥ 0.5 v/v	Birth/0 to 27 days old (Neonates) < 0.39 // or 40% > 0.61 // or 47% 28 days/1 month to 23 months old (Infants) < 0.29 // or 29% > 0.42 // or 42% 24 months/2 years to $< 16/18$ years old (Children, Adolescents) < 0.32 // or 32% > 0.47 // or 47%
RBC	≥ 6 TER/L	
Platelets	< 100 GIGAL ≥ 700 GIGAL	< 100 GIGAL > 700 GIGAL
ECG – PCSA criteria		
HR	< 50 bpm < 50 bpm and decrease from baseline ≥ 20 bpm < 40 bpm < 40 bpm and decrease from baseline ≥ 20 bpm < 30 bpm < 30 bpm and decrease from baseline ≥ 20 bpm	Birth/0 to 27 days old (Neonates) ≤ 90 bpm and decrease from baseline ≥ 20 bpm ≥ 190 bpm and increase from baseline ≥ 20 bpm 28 days/1 month to 23 months old (Infants) ≤ 80 bpm and decrease from baseline

Measures	Adult Criteria	Pediatric Criteria
	>90 bpm	≥20 bpm
	>90 bpm and increase from baseline ≥20bpm	≥175 bpm and increase from baseline
	>100 bpm	≥20 bpm
	>100 bpm and increase from baseline ≥20bpm	24 months/2 years to <6 years old (Children)
	>120 bpm	≤75 bpm and decrease from baseline
	>120 bpm and increase from baseline ≥20 bpm	≥20 bpm
		≥140 bpm and increase from baseline
		≥20 bpm
		6 to <12 years old (Children)
		≤50 bpm and decrease from baseline
		≥20 bpm
		≥120 bpm and increase from baseline
		≥20 bpm
		12 to 16/18 years old (Adolescents)
		≤50 bpm and decrease from baseline
		≥20 bpm
		≥120 bpm and increase from baseline
		≥20 bpm
PR	>200 ms	Birth/0 to 27 days old (Neonates) ≥120 ms
	>200 ms and increase from baseline ≥25%	28 days/1 month to 23 months old (Infants) ≥140 ms
	> 220 ms	24 months/2 years to <6 years old (Children) ≥160 ms
	>220 ms and increase from baseline ≥25%	6 to <12 years old (Children) ≥170 ms
	> 240 ms	12 to 16/18 years old (Adolescents) ≥180 ms
	> 240 ms and increase from baseline ≥25%	
QRS	>110 ms	Birth/0 to 27 days old (Neonates) ≥85 ms
	>110 msec and increase from baseline ≥25%	28 days/1 month to 23 months old (Infants) ≥85 ms
	>120 ms	24 months/2 years to <6 years old (Children) ≥95 ms
	>120 ms and increase from baseline ≥25%	6 to <12 years old (Children) ≥100 ms
		12 to 16/18 years old (Adolescents) ≥110 ms
QTc (either QTcF or QTcB)	Absolute values (ms)	Birth/0 to <12 years old (Neonates, Infants, Children) Absolute values (ms)

Measures	Adult Criteria	Pediatric Criteria
Sodium	
≤129 mmol/L
 
≥160 mmol/L
	
≤129 mmol/L
 
≥150 mmol/L

Potassium	
<3 mmol/L
 
≥5.5 mmol/L
	
Birth/0 to 27 days old (Neonates)
 
≤3.0 mmol/L
 
≥7.0 mmol/L
 
28 days/1 month to 23 months old (Infants)
 
≤3.5 mmol/L
 
≥6.0 mmol/L
 
24 months/2 years to 16/18 years old (Children, Adolescents)
 
≤3.5 mmol/L
 
≥5.5 mmol/L

Glucose		
Hypoglycemia	≤3.9 mmol/L and <LLN	<2.7 mmol/L
Hyperglycemia	
≥11.1 mmol/L (unfasted);
 
≥7 mmol/L (fasted)
	
≥7 mmol/L (fasted after >12 hours of fast);
 
≥10.0 mmol/L (unfasted)

Albumin	≤25 g/L	
Vital signs		
Heart rate	
≤50 bpm and decrease from baseline ≥20 bpm
 
≥120 bpm and increase from baseline ≥20 bpm
	
Birth/0 to 27 days old (Neonates)
 
≤90 bpm and decrease from baseline ≥20 bpm
 
≥190 bpm and increase from baseline ≥20 bpm
 
28 days/1 month to 23 months old (Infants)
 
≤80 bpm and decrease from baseline ≥20 bpm
 
≥175 bpm and increase from baseline ≥20 bpm
 
24 months/2 years to <6 years old (Children)
 
≤75 bpm and decrease from baseline ≥20 bpm
 
≥140 bpm and increase from baseline ≥20 bpm
 
6 to <12 years old (Children)
 
≤50 bpm and decrease from baseline ≥20 bpm
 
≥120 bpm and increase from baseline ≥20 bpm
 
12 to 16/18 years old (Adolescents)
 
≤50 bpm and decrease from baseline ≥20 bpm

Measures	Adult Criteria	Pediatric Criteria
Systolic BP	
≤95 mmHg and decrease from baseline ≥20 mmHg ≥160 mmHg and increase from baseline ≥20 mmHg
	
≥120 bpm and increase from baseline ≥20 bpm Birth/0 to 27 days old (Neonates) ≤60 mmHg and decrease from baseline ≥20 mmHg ≥85 mmHg and increase from baseline ≥20 mmHg 28 days/1 month to 23 months old (Infants) ≤70 mmHg and decrease from baseline ≥20 mmHg ≥98 mmHg and increase from baseline ≥20 mmHg 24 months/2 years to <6 years old (Children) ≤70 mmHg and decrease from baseline ≥20 mmHg ≥101 mmHg and increase from baseline ≥20 mmHg 6 to <12 years old (Children) ≤80 mmHg and decrease from baseline ≥20 mmHg ≥108 mmHg and increase from baseline ≥20 mmHg 12 to 16/18 years old (Adolescents) ≤90 mmHg and decrease from baseline ≥20 mmHg ≥119 mmHg and increase from baseline ≥20 mmHg

Diastolic BP	
≤45 mmHg and decrease from baseline ≥10 mmHg ≥110 mmHg and increase from baseline ≥10 mmHg
	
Birth/0 to 27 days old (Neonates) ≤34 mmHg and decrease from baseline ≥10 mmHg ≥50 mmHg and increase from baseline ≥10 mmHg 28 days/1 month to 23 months old (Infants) ≤34 mmHg and decrease from baseline ≥10 mmHg ≥54 mmHg and increase from baseline ≥10 mmHg 24 months/2 years to <6 years old (Children) ≤34 mmHg and decrease from baseline ≥10 mmHg ≥59 mmHg and increase from baseline ≥10 mmHg 6 to <12 years old (Children) ≤48 mmHg and decrease from baseline ≥10 mmHg ≥72 mmHg and increase from baseline ≥10 mmHg 12 to 16/18 years old (Adolescents) ≤54 mmHg and decrease from baseline ≥10 mmHg ≥78 mmHg and increase from baseline ≥10 mmHg

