2.1.4.3 Laboratory safety variables

Clinical laboratory data consist of blood analysis, including hematology, clinical chemistry, and urinalysis. Clinical laboratory values after conversion will be analyzed into standard international units and international units will be used in all listings and tables.

Blood samples for clinical laboratories will be taken as specified in the study protocol. The laboratory parameters will be classified as follows:

- Hematology: red blood cell count, hematocrit, hemoglobin, white blood cell count with differential count (neutrophils, eosinophils, basophils, monocytes, and lymphocytes), platelets,
- Biochemistry:
 - Plasma/serum electrolytes: sodium, potassium, chloride, calcium,
 - Liver function: aspartate aminotransferase (AST), alanine aminotransferase (ALT), alkaline phosphatase, gamma-glutamyl transferase, total and conjugated bilirubin,
 - Renal function: creatinine, blood urea nitrogen, uric acid,
 - Metabolic panel: glucose, albumin, total proteins, total cholesterol, triglycerides,
 - Potential muscle toxicity: creatine kinase, creatine kinase with MB fraction, lactate dehydrogenase.

Urinalysis will include urine color, appearance, specific gravity, proteins, glucose, erythrocytes, leukocytes, ketone bodies, and pH to be assessed:

- Qualitatively: A dipstick is to be performed on a freshly voided specimen for qualitative detection using a reagent strip.
- Quantitatively: A quantitative measurement for protein, erythrocytes, and leukocytes count will be required in the event that the urine sample test is positive for any of the above parameters by urine dipstick (eg, to confirm any positive dipstick parameter by a quantitative measurement).

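### SAP Table 15, pediatric criteria: the WBC rule for ages 2 to under 6 has no low limit, and the hemoglobin mmol/L limits use an unlabeled scale one quarter of the adult one

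*SAP*

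**What the plan says.** Table 15 in SAP Appendix A has an adult and a pediatric column. SAP 2.6 uses these criteria to decide which patients had at least one PCSA during the treatment epoch, and SAP 2.6.4 tabulates the laboratory incidences from them.

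**White blood cells.** The pediatric entry for 2 to under 6 years is ">3.0 GIGAL >16.0 GIGAL". The entries around it are:
- infants: "<4.0 GIGAL >20.0 GIGAL"
- 6 to under 12 years: "<5.0 GIGAL >17.0 GIGAL"
- 12 to 16/18 years: "<4.5 GIGAL >13.5 GIGAL"
- adults: "<3.0 GIGAL (non-Black), <2.0 GIGAL (Black), ≥16.0 GIGAL"

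**Hemoglobin.** For 2 to under 16/18 years the limit is given in two units, "1.55 mmol/L or 10.0 g/dL or any decrease", and the accompanying fall from baseline is 0.31 mmol/L or 2 g/dL. The adult column gives its fall from baseline as "20 g/L (1.24 mmol/L". No footnote says that the columns use different molar conventions.

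**Units.** SAP 2.1.4.3 states: "Clinical laboratory values after conversion will be analyzed into standard international units". It does not say whether hemoglobin is held in g/L or in mmol/L.

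**The concern.** A PCSA criterion is applied by a program, so a wrong sign or an unstated unit goes straight into the counts. The WBC entry has two greater-than signs and therefore no low side. The hemoglobin row assigns two mmol/L values to the same mass concentration, depending on the column.

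The trial admits patients from age 3 (protocol exclusion E 01), so both entries can apply. What is at stake is the accuracy of the pediatric flags in descriptive safety tables: false flags for WBC with low counts missed, and, under one choice of units, missed low hemoglobin with too many flagged falls. Pediatric data on avalglucosidase alfa also form a separate safety group (Group 4 in SAP 2.6), where a single flag is conspicuous.

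**Working it through.** **1. WBC, ages 2 to under 6.** Inputs are the Table 15 entries quoted above.
- As written, the rule is WBC > 3.0 or WBC > 16.0. The second condition lies inside the first, so the rule reduces to WBC > 3.0.
- A count of 2.0 is not flagged. A count of 8.0 is flagged.
- With the first sign reversed, the rule is WBC < 3.0 or WBC > 16.0. Then 2.0 is flagged and 8.0 is not.
- Reading the entry as two grades of severity, like the ALT rows, does not help. It would make everything above 3.0 a first grade and still leave no low limit.
- The neonatal (4.0 / 25.0), infant, 6 to under 12, 12 to 16/18 and adult WBC entries all give a low limit and then a high one. So do lymphocytes (below 1.0, above 9.5) and neutrophils (below 1.2, above ULN) for the same age band.

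**2. Hemoglobin scale.** For each pair printed in Table 15, factor = (mmol/L) / (g/L), with 1 g/dL = 10 g/L.

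| Column | g/L | mmol/L | Factor |
|---|---|---|---|
| Adult male, low | 115 | 7.14 | 0.06209 |
| Adult male, high | 185 | 11.48 | 0.06205 |
| Adult female, low | 95 | 5.9 | 0.06211 |
| Adult female, high | 165 | 10.24 | 0.06206 |
| Adult, fall | 20 | 1.24 | 0.06200 |
| Infant, low | 90 | 1.40 | 0.01556 |
| 2 to under 16/18, low | 100 | 1.55 | 0.01550 |
| 2 to under 16/18, fall | 20 | 0.31 | 0.01550 |

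- Adult mean factor: 0.06206. Pediatric mean factor: 0.01552. Ratio: 0.06206 / 0.01552 = 4.00.
- For the identical fall of 20 g/L: 1.24 / 0.31 = 4.00.
- Within each column the factor is constant, so each column reproduces its own figures. The columns differ only from each other.
- Pediatric limits on the adult scale: 100 × 0.06206 = 6.21 mmol/L and 20 × 0.06206 = 1.24 mmol/L.
- If adult-scale mmol/L data met the printed pediatric limits, 1.55 / 0.06206 = 25 g/L would be the low limit in place of 100 g/L, and 0.31 / 0.06206 = 5 g/L would be the fall in place of 20 g/L.

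The neonatal hemoglobin entry (86 mmol/L beside 12.0 g/dL) fits neither scale. It may be a reading fault and concerns an age that cannot be enrolled, so it is left out.

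**3. How many records.** In the blinded period, one wrongly flagged child is 1 of about 48 patients per arm (96 / 2), or 2.1%. For the pediatric group, the protocol adds up to 2 children directly to the open-label phase only if fewer than 4 were enrolled. If that provision was used as written, there are at most 3 + 2 = 5 children, and one flag is at least 1 / 5 = 20% of them.

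**The case against.** The strongest objection concerns the evidence for the WBC sign. It was read from text extracted from the PDF, and this table shows damage: unit slashes are lost, the neonatal hemoglobin figure looks wrong, and the two WBC entries for older children appear under the lymphocyte label. A misread sign is possible. That makes a check of the original PDF necessary. It does not supply a reading in which the extracted rule is sensible, and the less-than signs in the neighboring entries survived.

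The second objection is that hemoglobin is not a miscalculation. This stands. A reader might infer from the four-fold gap that the pediatric limits are themselves wrong, but they match the g/dL values printed beside them. The fault is a missing label, and harm needs data in mmol/L on the adult scale. No section says hemoglobin is held that way, and the adult column leads with g/L.

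Third, a reader might infer that particular children are misclassified or that safety conclusions are compromised. The documents do not support this. Age 3 is an entry floor, and nothing shows that anyone aged 3 to 5 was enrolled. SAP 1.1 expects few patients under 18. SAP 2.6 plans no inferential testing on safety data. Protocol 11.4.4.2 also classifies laboratory values against the laboratory's normal ranges, so a low count would still appear elsewhere.

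**Conclusion.** Both faults are in the table, and both are minor.

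The WBC entry for ages 2 to under 6, as it reads, cannot be the intended rule: it flags every count between 3.0 and 16.0, which the paired form would leave alone, and it flags no low count. This assumes that the PDF carries the same sign as the extracted text.

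The hemoglobin row mixes two molar scales that differ by a factor of 4.00. Used in g/dL or g/L, the pediatric limits work. Only if adult-scale mmol/L values are compared with them do the effective limits become 25 g/L and a fall of 5 g/L.

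The consequence is confined to descriptive PCSA counts in a handful of children at most. No efficacy result depends on these entries.

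**What to change.** Check the original PDF and the sponsor document cited as the source of Table 15 (SAP reference 29; PCSA version of May 2014). Then:
- WBC, 2 to under 6 years: change the first sign to less-than, giving below 3.0 or above 16.0 GIGA/L, provided the source confirms the number.
- Pediatric hemoglobin, 2 to under 16/18 years: give g/L only (below 100 g/L; fall of 20 g/L), or convert to the adult column's scale (6.2 mmol/L; 1.24 mmol/L).
- State in a table footnote the hemoglobin unit used for analysis and, if it is mmol/L, the molar convention.

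The cost is a few table entries and a matching check of the PCSA program. SAP 1.6 already records a correction of this kind in the same appendix, for children's diastolic blood pressure. Without it, the programmer must either code an illogical rule or correct it with no record. These are analysis flags, so no rule for managing patients changes.
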